7.1 Data Management	13
7.2 Procedures for Prevention and Addressing Breaches of Confidentiality.....	13
7.3 Data Capture Methods	14
7.4 Types of Data.....	14
8.0 Laboratory Specimens	15
8.1 Laboratory Specimens	15

9.0	Safety Monitoring and Adverse Event Reporting.....	16
9.1	Data Management, Analysis, and Quality Assurance Plan.....	16
9.2	Specification of Safety Parameters	16
9.2.1	Adverse Events	16
9.2.2	Serious Adverse Events	17
9.2.3	Relationship to study intervention	17
9.2.4	Severity of Event.....	17
9.3	Reporting Procedures.....	18
9.3.1	Serious Adverse Event Reporting	18
10.0	Statistical/Analytic Considerations.....	18
10.1	Primary Outcome	18
10.2	Power to Detect Effects in Primary Outcome.....	18
10.3	Preliminary Efficacy Assessment	19
10.4	Theoretical Assessments	19
11.0	Human Subjects Considerations	19
11.1	Ethical Review	19
11.2	Informed Consent.....	20
11.3	Risks to Participation	20
11.3.1	Risks to Study Participation.....	20
11.3.2	Additional Risks for Participants on PrEP.....	21
11.4	Benefits to Subject or Future Benefits	21
11.5	Compensation	22
11.6	Participant Privacy and Confidentiality	22
12.0	Administrative Procedures.....	22
12.1	Quality Assurance	22
12.2	Regulatory Requirements.....	22
13.0	References.....	24

PROTOCOL TEAM ROSTER

Principal Investigators:

[name] (Contact PI)
Associate Professor
Department of Behavioral Sciences and Health Education
Rollins School of Public Health, Emory University
[name]
[contact] Email: [contact]

[name] DVM
Professor
Department of Epidemiology
Rollins School of Public Health, Emory University
[name]
[contact] Email: [contact]

Co-Investigators:

[name]
Chief Medical Officer
BlueD
[name]
Beijing, China
[contact] Email: [contact]

[name]
Assistant Professor
Department of Epidemiology
University of North Carolina, Chapel Hill
[name]
[name]

[name]
Associate Professor
Department of Biostatistics and Bioinformatics
Rollins School of Public Health, Emory University
[name]
[contact] Email: [contact]

SCHEMA

Principal Investigator: [name]

Purpose:

The overarching objective is to assess feasibility and acceptability of Blued+, a combination HIV prevention intervention that will integrate a combination package of HIV prevention services into the Blued mobile application (app) platform, for men who have sex with men (MSM) in China.

Study Design:

The pilot study will be an interrupted time series cohort of 400 MSM. In two cities, a three-month baseline standard of care (SOC) period with measurement at 0 and 3 months will be followed by a 12-month intervention period with the measurement at 6, 9, 12, and 15 months. The longitudinal design will allow for 1) assessment of feasibility and acceptability outcomes, 2) development of the logistical and operational needs to provide the app-based intervention, and 3) development of estimates for key parameters to design a future, definitive study to determine intervention efficacy.

Standard of care will consist of the existing Blued app and local health services. Blued app access currently includes health education components such as information regarding HIV testing and pre-recorded health messages from Chinese celebrities. Participants will have access to in-person no-cost services for HIV testing and condom pick-up from local non-governmental organizations (NGOs) that support MSM in both cities.

At three months, participants will be provided with educational materials in the health portal as well as theory-based HIV prevention messages, along with home HIV test kits and condoms. This intervention will have a health portal that houses all HIV prevention functionalities. The exact nature of the interventions included will be further defined by the qualitative work, as additional services may be identified as essential to an HIV prevention package in China. These may include services such as peer support or stigma reduction. Additionally, participants will receive PrEP medication, laboratory, and care costs free of charge.

In the portal, users will be able to explore health-supporting functions of the app and access offline services, including behavioral risk assessments, an HIV prevention platform, HIV testing, linkage to care for those testing positive for HIV, in-app screening and referral to HIV pre-exposure prophylaxis (PrEP) and sexually transmitted infection (STI) services, and provision of PrEP with emtricitabine/tenofovir disoproxil fumarate (FTC/TDF).

Study Population:

The study population will be self-reported HIV-negative Blued users who are 18 years of age or greater, were assigned a male sex at birth, report having anal sex with a man in the last 6 months, are able to complete a survey in standard Mandarin Chinese, are willing to provide two forms of contact information, are willing to update the Blued app with the Blued+ portal after the baseline period, are willing to complete quarterly surveys for the 15-month study period, and reside in metropolitan Beijing or Chengdu, China.

Study Size:

The sample for the pilot study will consist of approximately 400 MSM, 200 each in Beijing and Chengdu. All 400 men will be followed for 15 months.

Study Duration:

Recruitment activities will be conducted for three months or until 200 MSM have been recruited in each intervention city. After enrollment, MSM will have a follow-up period of 15 months for each participant.

Primary Objectives:

This study has four primary objectives:

1. Conduct a review of literature on behavioral and biomedical interventions offered in online and offline settings for MSM in China.
2. Develop a mathematical model of HIV transmission in Chinese MSM, informed by annual cross-sectional surveys, that accounts for behavioral, structural, and biological factors in order to estimate the impact of different scenarios of intervention provision and inform selection of intervention components for the pilot study.
3. Assess Blued+ intervention feasibility and acceptability in China, first by collecting qualitative data to inform the development of the Blued+ app components and service delivery and then by developing and pilot testing Blued+ among MSM in Beijing and Chengdu, China. This protocol includes only the pilot study portion of the overall study.
4. Use preliminary information from the pilot study to design a larger, definitive study of the efficacy of the prevention package for Chinese MSM.

1.0 INTRODUCTION

Background and Rationale

HIV disproportionately affects the estimated 21 million men who have sex with men (MSM) who live in China.^{1,2} The high impact of HIV among MSM has been recognized for nearly 2 decades, since the documentation of a high prevalence of HIV among MSM donating blood.³ In a survey of 47,000 Chinese MSM in 61 cities, the prevalence of HIV was 4.9%; higher prevalence of HIV was reported in MSM who were non-local or met sex partners through the internet.⁴ A national meta-analysis in 2014 reported a pooled 6.5% prevalence of HIV among MSM.⁵ In Beijing, a cohort study of MSM documented annualized incidence of 7.8% -- a level sadly similar to intense HIV epidemics among MSM in Thailand⁶, South Africa, and the United States⁷. In China, the estimated incidence of HIV was higher for MSM than for people who inject drugs (PWID), female sex workers, and male patients attending sexually transmitted infection (STI) clinics.⁸ According to data from the Chinese National Sentinel Surveillance System, from 2010-2014, the HIV prevalence among MSM increased substantially, from 5.7% to 7.8%.⁸ MSM in China represented 12% of new case diagnoses in 2010, and 26% of new case diagnoses in 2014.⁹ Similarly, a series of cross-sectional surveys in Guangxi documented a doubling of HIV prevalence among MSM from 2008-2012.¹⁰ To inform this proposal, our Emory/Blued team recently completed a survey of over 4,000 MSM in four cities, including the two proposed pilot cities. In this sample of Blued users, self-reported HIV prevalence among those who had tested for HIV was 12.5% (406/3256) overall, with 9.3% (162/1746) in Beijing and 19% (137/724) in Chengdu.

Despite the substantial epidemic, the use of HIV prevention services among MSM is low. In the 61-city survey, over half of the sample reported inconsistent condom use with male partners in the prior year.⁴ In our four-city data, 46% (1584/3457) of sexually active MSM reported inconsistent condom use. Although sexually transmitted infection (STI) control is a priority in China's HIV prevention plan¹¹, less than a third of MSM in China have ever been tested for syphilis,¹² and our four-city survey found that only 30% had tested for any STI in the past year. In terms of HIV testing, a systematic review in 2014 documented an annual period prevalence of HIV testing of 38% among MSM in the most recent reporting period,¹³ and our four-city survey found 52% annual testing prevalence. Taken together, these data suggest the need for improved coverage of each step of the HIV prevention continuum, including the promotion of HIV testing, increased condom uptake, and screening for STIs.

Primary reasons for low levels of HIV testing include privacy concerns and nondisclosure of sexual identity; these problems are readily addressable through home-based services. Several studies have found privacy concerns are an important barrier to HIV testing among Chinese MSM,¹⁴⁻¹⁶ with one finding it the most universally agreed upon consideration.¹⁵ Privacy concerns are likely related to the relatively low levels of sexual orientation disclosure,¹⁷ which is also independently associated with lower likelihood of HIV testing.^{15,17,18} For individuals who wish to maintain privacy, or to avoid potential disclosure of their sexual identity to clinicians or service providers, home services for HIV prevention may be a good option. One study found 57% of their sample was interested in home HIV testing,¹⁵ and our four-city study found that 66% of Blued app users would order a home HIV test kit from the app if it were offered.

Patterns of migration are also uniquely important in China. For men who are living outside of their registered home district (hukou), access to health services might be more challenging;¹⁹ these men were also the group with the highest HIV prevalence in China.⁴ Hukou-migrating MSM often move between multiple cities, suggesting the need for a mobile system to organize reminders and to find new local health service in different cities. Stigma and discrimination are frequently anticipated and experienced by MSM, and perceived discrimination is associated with lower uptake of testing.²⁰ Further, MSM who reported being less engaged in gay communities have lower uptake of prevention services.¹² Thus, coordinating HIV prevention services through a mobile app might help reach critical populations of

MSM, including hukou-migrating MSM and those who may be less engaged in their communities. Men who experience stigma and who are less engaged in their communities may turn to the internet to meet partners. Delivering services online, where the highest risk men meet their partners, is responsive to the context of the Chinese epidemic among MSM and will reach MSM who would otherwise be hidden to public health efforts.

Blued is a geosocial networking (GSN) app for MSM, developed in China by a community-based organization (Danlan). The app has grown rapidly in popularity both in China and throughout the Asian Region. In 2018, Blued had 12 million active users each month, including over 480,000 in Beijing, 221,000 in Chengdu, 115,000 in Kunming, and 174,000 in Tianjin. The large user base is impressive, particularly when considering that the total population of MSM in the United States is estimated at 4.5 million.²¹ Blued is a socially conscious community-based organization, providing prevention information through a team led by [name], a Chinese physician. Previous efforts have included public health information and prevention messages through advertisements, and providing information on the locations of HIV test sites. Blued has conducted a number of large surveys of MSM,^{12,17,18} including the Emory/Blued survey, illustrating the willingness of MSM to participate in data collection through the Blued app.

Modeling conducted by our previous MP3 project,²² and other models from our work in the US and India,^{23,24} have illustrated that PrEP²⁵ is a critical component of comprehensive prevention packages for MSM. Daily oral emtricitabine / tenofovir DF (FTC/TDF) for PrEP can provide >99% reduction in risk of HIV acquisition.²⁶ Yet even in the context of PrEP availability and uptake, our models have demonstrated that offering a package that includes other prevention modalities like HIV testing and condom promotion can contribute to substantial reductions in HIV incidence.²² Despite its high efficacy, PrEP is not currently approved by China FDA. Additional data, including modeling data to demonstrate PrEP's potential impact in China and the feasibility of providing PrEP to Chinese MSM, will be important for eventual regulatory approval (see letter of support, NCAIDS).

Our scientific premise is that the HIV prevention services continuum for MSM needs to be stronger, and that integrating recommendations and direct linkages to services into a mobile app already used by Chinese MSM will be a feasible and acceptable way to increase coverage of basic prevention services. This research will be grounded in the experiences of Blued in China and the experiences of the US-based team in mHealth and app-based delivery of at-home HIV test kits and PrEP programs. We therefore propose to test the provision of a package of prevention services, optimized for Chinese MSM based on a literature review, epidemic modeling and community input that will be delivered through Blued – a GSN app that offers the potential to reach millions of Chinese MSM.

2.0 STUDY OBJECTIVES

2.1 Overarching Objective

The overarching objective of the pilot study is to evaluate the feasibility and acceptability of Blued+, a combination HIV prevention intervention that integrates a combination package of HIV prevention services into the Blued app platform.

The pilot study is Phase III of a larger project. Phase I consists of a comprehensive literature review and summary of current knowledge of HIV prevention interventions for MSM in China. The review will focus on (1) identifying successful interventions and programs related to PrEP or mobile apps, and characterizing components of the interventions that made them successful and (2) describing components of the HIV epidemic in China, including key parameters that could inform mathematical modeling. This review will also serve to provide inputs for the Phase III pilot study.

Phase II includes the development of a mathematical model of HIV transmission in Chinese MSM. This modeling will be used to estimate the potential impact of scaling up different combinations of HIV prevention packages for Chinese MSM. Further, this modeling will be used to inform the pilot study through identifying the most efficacious combinations of interventions, and by identifying leverage points for the success of key interventions that are likely to be a part of the final package.

Phase III includes both qualitative studies as well as the pilot study. Qualitative work (focus group discussions and in-depth interviews) will be used to identify acceptable and optimal HIV prevention interventions for MSM in China to include as components of the prevention package through Blued+. This qualitative work is described in a separate protocol. The pilot study will include biological and behavioral data collection to monitor the uptake of the prevention interventions by study participants. These activities are described here, though additional services may be identified as essential to an HIV prevention package in China during modeling and literature review from Aims 1 and 2, e.g. peer counseling or stigma reduction.

2.2 Specific Aims

This study will have the following four specific aims:

Aim 1. Conduct a review of literature on HIV prevention interventions offered in online and offline settings for MSM in China.

Aim 2. Develop a mathematical model of HIV transmission in Chinese MSM, informed by annual cross-sectional surveys, that accounts for behavioral, structural, and biological factors in order to estimate the impact of different scenarios of intervention provision and inform selection of intervention components for the pilot study.

Aim 3. Assess Blued+ intervention feasibility and acceptability in China.

Aim 3.1. Collect qualitative data, through activity-based focus groups and user experience cognitive interviews to inform development of Blued+ app components and service delivery.

Aim 3.2. Develop and pilot test Blued+ among 400 MSM in Beijing and Chengdu, China.

Aim 4. Use preliminary information from the pilot study to design a larger efficacy trial of the prevention package for Chinese MSM.

3.0 STUDY DESIGN

This study is an interrupted time series pilot study designed to assess feasibility and acceptability of several interventions to encourage uptake and adherence of PrEP. Per the NIH definition of clinical trial case studies, including 18F and 29, this study is not a clinical trial. In this study, a novel HIV combination service package, the Blued+ portal, will be delivered through a widely accessed geospatial networking app Blued. Intervention development, in terms of the selection of intervention components, the relative emphasis placed on each component, and the manner in which the components are offered will be informed by a literature review (Aim 1), mathematical modeling (Aim 2), and qualitative data collection (Aim 3.1). Blued+ will include all functionality of Blued (which attracts geosocial network users), and it will include a suite of HIV prevention services. These services may include risk screener quizzes, home

HIV test kits, and referral for PrEP provider visits and associated laboratory testing. In addition to these services, the study will include:

Educational materials focused on PrEP as well as other sexual health topics. Educational materials will be built into the health portal. Topics of education may include an overview of PrEP and PrEP medication, the effectiveness of PrEP, PrEP payment, side effects, stigma, and where to access PrEP, among other topics related to prevention of HIV and STIs.

Additionally, participants will receive theory-based sexual health and prevention messages delivered via the Blued+ app. These messages will be developed using social cognitive theory with the goal of creating a comprehensive messaging package to improve participants' self-reported sexual health and prevention behaviors, beliefs, and attitudes. Participants will also receive a screener quiz that allows them to assess whether PrEP is right for them and encourage them and link to PrEP care. Those participants who do choose to initiate PrEP will receive PrEP medication (FTC/TDF), associated laboratory testing, and clinical care free of charge.

Participants will be encouraged to schedule a visit with a study provider in each intervention city in person or online, and will access PrEP free of charge through these study clinics.

A total of 400 participants will be enrolled in the intervention with quarterly follow-up with a total of six surveys for each participant comprising enrollment/baseline (two surveys) and pilot intervention (four surveys). The survey will be team translated to ensure accuracy of the text and participant understanding.

Below is a diagram of the pilot study design:

[figure not shown]

Figure 1 Pilot Study Design Overview

3.1 Study population

The study population includes registered Blued users who self-report male sex at birth, are age 18 years or older, who report anal sex with a man in the past 6 months, behaviorally eligible for PrEP, and who do not report an HIV diagnosis. Eligible men will be residents of metropolitan areas of Beijing or Chengdu, China.

3.2 Sample Size

Over the entire study period, 400 participants will be enrolled in the prospective pilot study intervention. All participants will be followed longitudinally for 15 months.

4.0 SELECTION OF STUDY PARTICIPANTS

4.1 Inclusion Criteria

Participants must meet all inclusion criteria to participate in this study. These inclusion criteria include:

1. Registered Blued app user
2. ≥ 18 years of age
3. Male sex at birth
4. Self-report anal sex with a man in the last 6 months
5. HIV-negative or unknown HIV status
6. Behaviorally eligible for PrEP per published China guidance
7. Able to complete study instruments in Mandarin Chinese
8. Resident of the metropolitan area of Beijing or Chengdu, China

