4.2 Exclusion Criteria

Potential participants meeting any of the exclusion criteria at baseline will be excluded from participating in any part of the study. The exclusion criteria for this study include:

1. Not a registered Blued app user
2. < 18 years of age
3. Not male sex at birth
4. Does not report anal sex with a man in the last 6 months
5. Has previously tested positive for HIV
6. Not eligible for PrEP per published China guidance
7. Unable to complete study instruments in Mandarin Chinese
8. Not a resident of the metropolitan area of Beijing or Chengdu, China
9. Currently enrolled in another HIV prevention study
10. Evidence of fraudulent participation, such as a duplicate IP address, multiple screening attempts, duplicate emails, etc.

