5.4 PrEP

5.4.1 Additional Inclusion/Exclusion Criteria for Participants electing PrEP

In addition to the inclusion and exclusion criteria above for participants who enter the study, additional inclusion and exclusion criteria apply to participants who initiate PrEP. These criteria are based on US CDC Guidelines for PrEP or Chinese recommendations if available. All participants who choose to initiate PrEP through this study will be required to meet these guidelines, including laboratory testing.

Inclusion Criteria:

In addition to the inclusion criteria above, the inclusion criteria for PrEP are:

1. Laboratory confirmed **HIV-negative**
2. Behaviorally indicated for PrEP, including any of the following:
 - a. History of inconsistent or no condom use with more than one partner
 - b. History of inconsistent or no condom use with one partner who is not mutually monogamous
 - c. Sexual partner living with HIV who is not virally suppressed
 - d. History of a sexually transmitted infection by lab testing or self-report in the past six months
 - e. Use of post-exposure prophylaxis
 - f. Engagement in transactional sex, including sex work
 - g. Requesting PrEP
 - h. Other criteria as determined by future guidance from China
3. No contraindications to emtricitabine/tenofovir disoproxil fumarate (FTC/TDF)
4. **Creatinine clearance** of at least 60 mL/min reported by a laboratory or estimated using the Cockcroft-Gault Equation:

$$CrCL \text{ (mL/min)} = \frac{(140 - \text{age}) * \text{body weight [kg]}}{\text{Serum Cr [mg/dL]} * 72}$$

5. Willing to adhere to a PrEP dosing regimen
6. Willing to attend PrEP maintenance visits every 3 months

Exclusion Criteria

In addition to the exclusion criteria above, the exclusion criteria for PrEP are:

1. HIV-positive, either laboratory confirmed or by self-report
2. Signs or symptoms of acute HIV infection, probably recent exposure to HIV
3. **Chronic hepatitis B**
4. Creatinine clearance <60 mL/min
5. Symptoms of acute HIV infection within the prior 30 days
6. Contraindications to emtricitabine/tenofovir disoproxil fumarate (FTC/TDF)
7. Unwilling to attend PrEP maintenance visits every 3 months

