6.0 MEASURES

A summary table of study measures, and sources for each measure, are provided in the table below. Measurement of tenofovir-diphosphate (TFV-DP) levels will be conducted using liquid chromatography/tandem mass spectrometry methods on DBS samples. TFV-DP level can be translated to an interpretation that indicates mean number of days per week PrEP is ingested over a period of approximately one month. The cutpoint used will be TFV-DP levels considered a surrogate for substantial protection: >700 fmol/punch, a level indicating >4 doses/wk.

Construct	Measure	Data source	Definition	Analysis
PRIMARY OUTCOMES				
Feasibility	Home HIV test orders	Order fulfillment	Proportion of participants sent a home HIV test	Benchmark ≥ 30%
Feasibility	Condom orders	Order fulfillment	Proportion of participants sent 'choice' condom package	Benchmark ≥ 30%
Feasibility	PrEP initiation	Clinical site data	Proportion of participants receiving a PrEP prescription	Benchmark ≥ 20%
Acceptability	Systems Usability Scale ^{126, 127}	Survey	10-item scale, good score is >71	Benchmark: Good score (≥ 71 out of 100)
Acceptability	Ratings for intervention components ⁷²	Survey	Likert acceptability rating for each intervention component (e.g. home HIV test)	Benchmark: Acceptable ratings (≥ 3 out of 5)
PRELIMINARY EFFICACY ASSESSMENT				
HIV testing	HIV testing ^{44,128}	Survey	Change in median number HIV tests	GEE model
Condom use	Condom use ^{44,128}	Survey	Change in proportion of participants reporting always using condoms for anal sex	GEE model
PrEP Use	PrEP use ¹²³⁻¹²⁵	Laboratory data	Number participants with protective levels of TDF-DP	Descriptive report
THEORETICAL ASSESSMENT				
Prevention cascade	PrEP cascade levels ¹²⁹	Survey and clinical site data	PrEP awareness, willingness, prescription, persistence in care, and medication adherence	Descriptive and logistic regression
Theoretical assessment	Unified Theory of Acceptance and Use of Technology (UTAUT2) ¹²¹	Survey	Validated items for performance expectancy, effort expectancy, social influence, hedonic motivation, and habit.	Descriptive and GEE model to estimate SEM parameters
PROCESS OUTCOMES				
Process	New HIV testers	Survey	Proportion changing from never to ever HIV test	Descriptive report
Process	New condom users	Survey	Proportion changing from none to some condom use	Descriptive report
Process	Visits to local health clinics	Survey	Proportion receiving HIV services at health departments	Descriptive report

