10.3 Preliminary Efficacy Assessment

Preliminary efficacy assessments will describe differences in outcomes for the intervention, compared to the baseline period, for the median number of HIV tests and the proportion reporting all anal sex acts as condom-protected. A generalized estimating equations (GEE) repeated measures analysis will be conducted for the binary outcome of HIV testing (test/not testing). The GEE model will contain the seven time periods with primary comparisons of 0-month (first baseline) measurement to 6-month (end wash-out baseline period measurement and to 12-month (end first intervention period) measurement. Time will be considered as a fixed effect to compare proportion tested across intervals, with a random intercept for individuals. A similar GEE model will be conducted for the condom outcome (always/not always condom use). Logistic regression models will be fitted to understand PrEP cascade progressions, with the main analysis being any forward progress (yes/no) in the overall cascade between 0-month and 15-month measurements. These analyses will consider variables of progression in the PrEP cascade. Time at which cascade progress was made (e.g. 3 months) will be entered as a co-variate. A multifaceted approach to address missingness for our outcomes will be used. Primary analyses will treat values as missing at random. Sensitivity analyses will re-analyze data using both last-value-carried-forward and multiple imputation methods.

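### The condom-use comparisons start from month 0, the survey closest to selection on PrEP-indicating behaviour, so regression to the mean may be read as an intervention effect

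*Combined protocol and SAP*

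**What the plan says.** **Entry.** Section 4.1 requires men to be "Behaviorally eligible for PrEP per published China guidance", and Section 4.2 excludes those who are "Not eligible for PrEP per published China guidance". Section 3.1 repeats the requirement. The guidance itself is not set out.

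**Indications.** The only list of behavioural indications is in Section 5.4.1. Its first item is "History of inconsistent or no condom use with more than one partner" and its second is similar. Any one item is enough.

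**Timing of selection.** Section 4.3 describes a short screener. Section 5.0 lists rescreening and the baseline survey as separate baseline procedures. Section 5.3.1 adds that the baseline survey also assesses PrEP indication.

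**Outcome.** Section 6.0 defines the condom measure as "Change in proportion of participants reporting always using condoms for anal sex".

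**Analysis.** Section 10.3 names "primary comparisons of 0-month (first baseline) measurement to 6-month" and also month 0 to month 12, and extends a similar model to condom use.

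**Design.** The Schema describes one cohort with no control arm, surveyed at months 0 and 3 under standard of care and at months 6, 9, 12 and 15 under the intervention. Regression to the mean is not mentioned.

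**The concern.** When people are selected because of a recent behaviour that varies over time, the measurement nearest to selection tends to be atypical, and later ones drift back towards each person's usual level. Here the behaviour that probably helps to qualify a man is close to the opposite of the condom outcome, and the reference survey is the one taken nearest to qualification. With no control arm, nothing in the named comparisons separates this drift from an effect of Blued+.

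Section 10.2 says these analyses will draw on the interrupted time series design and inform a later trial, and the Schema and Aim 4 give the pilot the same purpose. A condom effect inflated by selection would be a poor input to that trial. The safeguard has already been collected: month 3 is the one survey after selection and before Blued+, but neither named comparison uses it as reference.

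**Working it through.** **Inputs from the documents.** N = 400 (Section 3.2). Section 1.0 reports "46% (1584/3457) of sexually active MSM reported inconsistent condom use". Check: 1584/3457 = 45.8%, which rounds to 46%. So always-use in that four-city sample is π = 1 − 0.458 = 0.542.

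**Assumptions (not in the documents).** s is the share of enrollees who qualified through inconsistent condom use; the rest have always-use π throughout. φ is the within-man correlation between two survey reports. The true intervention effect is zero.

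**Case A: the month-0 report coincides with the selecting report.** Always-use at month 0 is (1 − s)π. Expected rise to a later survey = (1 − φ)[π − (1 − s)π] = sπ(1 − φ). In percentage points:

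| s | φ = 0.4 | φ = 0.6 | φ = 0.8 |
|---|---|---|---|
| 0.3 | 9.8 | 6.5 | 3.3 |
| 0.5 | 16.3 | 10.8 | 5.4 |
| 0.7 | 22.8 | 15.2 | 7.6 |
| 0.9 | 29.3 | 19.5 | 9.8 |

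Chance of p < 0.05 with no effect, by a paired-difference z-test on 400 completers, at s = 0.3 and φ = 0.8:
- Probability of moving to always: 0.3 × 0.542 × 0.2 + 0.7 × 0.542 × 0.458 × 0.2 = 0.0673.
- Probability of moving away: 0.0348.
- Difference d = 0.0325; SE = √[(0.0673 + 0.0348 − 0.0325²)/400] = 0.0159; z = 2.05; chance about 53%.

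That is the lowest value in the grid; the highest is about 100%.

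**Case B: selection on a separate screener.** Let r₀ and rₜ be the screener's correlations with month 0 and with month t. Spurious rise = sπ(r₀ − rₜ). From month 0 to month 12, in points:

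| s | 0.6 → 0.6 | 0.8 → 0.6 | 0.9 → 0.5 | 0.9 → 0.4 |
|---|---|---|---|---|
| 0.3 | 0 | 3.3 | 6.5 | 8.1 |
| 0.5 | 0 | 5.4 | 10.8 | 13.5 |
| 0.7 | 0 | 7.6 | 15.2 | 19.0 |
| 0.9 | 0 | 9.8 | 19.5 | 24.4 |

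**Sensitivity to 54%.** Write the Case A rise as (1 − φ)(L − m₀), where L is enrollees' long-run always-use and m₀ is their always-use at month 0. With m₀ = 0.30 and φ = 0.7, L = 0.542 gives 0.3 × 0.242 = 7.3 points. L = 0.30 gives 0.

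**Month 3 as reference.** In Case B with s = 0.5 and correlations 0.9, 0.7 and 0.5 at months 0, 3 and 12:
- From month 0: 0.5 × 0.542 × 0.4 = 10.8 points.
- From month 3: 0.5 × 0.542 × 0.2 = 5.4 points.

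**A double difference does not work.** The contrast (month 6 − month 3) − (month 3 − month 0) looks attractive. If regression is complete by month 3, its first bracket is 0 and its second is the whole artefact, so the contrast equals minus the artefact. With 20% always-use at month 0 and φ = 0.7, that is −0.3 × (0.542 − 0.20) = −10.3 points.

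**The case against.** **The entry condition is inferred.** Section 5.4.1 says that "additional inclusion and exclusion criteria apply to participants who initiate PrEP", so its list is not the enrolment rule. Any single item suffices, one being simply "Requesting PrEP", and the condom items carry no look-back period. The Schema's population description does not mention PrEP eligibility. This stands: a reader might infer that every enrollee is an inconsistent condom user, making the outcome the exact complement of the entry rule, and the documents do not support that.

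**Selection is not made on the month-0 survey.** A reader might also infer that one measurement both selects men and serves as baseline. Sections 4.3 and 5.0 describe a screener and a rescreen apart from the survey. If these correlate equally with month 0 and later surveys, the bias is zero. This stands as a possibility. But rescreening and the survey are both baseline procedures, and reports made close together would normally agree better than reports 6 to 12 months apart.

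**The month-3 data are already in the model.** Section 10.3 fits all time points and speaks of comparison with the baseline period. If its first contrast is meant to end at the close of baseline, the corrected contrast is 0 versus 3 months, which is an estimate of drift. Even so, the 12-month comparison still starts from month 0.

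**The outcome is secondary.** Condom change is a preliminary efficacy measure. Section 10.1 makes feasibility and acceptability primary, Section 10.2 claims no power for change from baseline, and nothing says the condom estimate will size the later trial. This limits the importance of the point. Lack of power does not excuse avoidable bias, however.

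**Conclusion.** The point holds in a limited form. Entry on behavioural PrEP eligibility, no control arm and a month-0 reference together mean that regression to the mean may appear as an improvement in condom use. The documents do not support saying that it will.

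The size cannot be fixed. It is zero if the screener correlates equally with month 0 and later surveys, or if enrollees' long-run always-use is as low as their month-0 level. It exceeds 20 points where most men qualified through condom use and correlation falls steeply. All these figures rest on assumed shares and correlations, and the non-zero ones also on the 54% from a general sample rather than from PrEP-eligible men. The half-widths of 4 to 5 points in Section 10.2 are for single proportions, so they are only a loose yardstick for a paired change.

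The feasibility and acceptability conclusions are unaffected. The change is worth making because the data to reduce the bias are already planned.

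**What to change.** In Section 10.3, for the condom outcome:

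- Make the month-3 standard-of-care survey the reference for the intervention-period contrasts, for example 12 versus 3 months.
- Report the 0-to-3-month change as the estimate of regression to the mean plus background drift before Blued+.
- Label any contrast that starts from month 0 as secondary.
- Do not use the double difference (6 − 3) − (3 − 0), which over-corrects if regression is complete by month 3.
- State the recall window of the condom question, which the documents do not give. If it exceeds three months, month-3 answers reach back before entry and the gain is smaller.

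Make the change when Section 10.3 is reconciled with the design. It counts seven time periods and ends the baseline at month 6, whereas the Schema ends the baseline at month 3 and Sections 3.0 and 11.5 give six surveys. Correcting the months alone would leave month 0 as the reference for the 12-month comparison.

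**Cost.** SAP wording and contrasts from a model already planned, with no new data. A single reference survey gives slightly wider intervals than a pooled baseline, and the headline change will probably be smaller.
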